5.5 General Concomitant Medication and Supportive Care Guidelines

Because there is a potential for interaction of TPI 287 with other concomitantly administered drugs through the cytochrome P450 system, the use of drugs or herbal supplements that are known to be strong inhibitors/inducers of CYP3A4 and CYP2C8 are not permitted (Appendix B).

Prophylactic use of corticosteroids is allowed during the study to limit symptoms from metastases or radiation.

Non-enzyme inducing anti-epileptic drugs may be utilized to control or prevent seizures.

Principal Investigator should be alerted if the patient is taking any agent known to affect or with the potential to affect selected CYP450 isoenzymes.

5.6 **Duration of Therapy**

Patients will receive TPI 287 on days 1, 8, and 15 (total of 3 doses). On day 1, the TPI 287 will be administered 4 (+/-2) hours prior to FSRT.

5.7 **Duration of Follow Up**

Patients will be seen in follow-up on the 3rd, 6th, 9th, 12th, 15th, and 18th month following the first day of treatment with TPI 287. Patients will be followed for 18 months after first treatment on study or until death, whichever occurs first.

The following will be obtained at pre-treatment evaluation and at each follow up visit: Symptoms history, vital signs/ height and weight, physical examination, KPS/ECOG score, Mini-Mental State Examination, steroid use, quality of life questionnaire, and toxicity evaluation.

Radiologic assessment, MRI brain with and without gadolinium, will be performed at pretreatment and every three months following the end of treatment until the patient is off-study or reaches the 18 month study completion date.

Furthermore, the principal investigator will have close collaboration with oncologists treating the systemic malignancy. Information regarding the status of systemic malignancy such as results of standard imaging evaluations, serum biomarkers measurements, and systemic treatments will be collected and recorded at each visit.

5.8 Criteria for Removal from Study

Patients will be removed from study when any of the below criteria applies:

- Disease progression requiring therapy not allowed in the protocol, including whole brain radiation.
- Intercurrent illness that prevents further administration of treatment: a condition, injury, or disease unrelated to cancer, that renders TPI 287 or radiation treatment unsafe or regular study visits impossible, including, but not limited to, active infection, symptomatic congestive heart failure, unstable angina pectoris, cardiac arrhythmia, pregnancy, or psychiatric illness that would limit compliance with study requirements.
- Unacceptable adverse event(s) (see adverse events)
- Patient decides to withdraw from the study
- General or specific changes in the patient's condition that render the patient ineligible for the study
- Non-compliance with study treatment or protocol-required evaluations and study visits
- Inability of subject to comply with study requirements
- Determination by the investigator that it is no longer safe for the patient to continue therapy
- Patient who inadvertently becomes pregnant (see reporting of pregnancy)

Patients may withdraw at any time or be dropped from the study at the discretion of investigator should any untoward effects occur. In addition, a patient may be withdrawn by the investigator if he/she violates the study plan or for administrative and/or other safety reasons. The investigator or study coordinator must notify Cortice Biosciences immediately when a patient has been discontinued/withdrawn due to a serious adverse experience. All trial treatment-related toxicities and SAEs at the time of discontinuation/withdrawal should be followed until resolution or stabilization. Patients who are discontinued from the study will still be followed for disease progression.

All deaths that occur within the trial period or within 30 days after administration of the last dose of trial drug must be reported to Cortice Biosciences for the purposes of serious adverse event (SAE) reporting; however, deaths due to progression are not SAEs.

Patients who discontinue from the study for reasons unrelated to the study (e.g., personal

reasons, or adverse events after registration but prior to receiving study therapy) may be replaced as required for the study to meet its objective. The replacement will generally receive the same treatment or treatment sequence (as appropriate) as the allocation number replaced.

5.9 Stopping Rules

The expected rate of neurologic death with FSRT alone is 13-14%. ^{24,25} The reported rate for symptomatic radiation necrosis is 7.7%. ²⁴ A higher rate of neurologic death (> 14%) or symptomatic brain necrosis (> 10%) in this study would imply that the combination of FSRT and TPI 287 is excessively toxic and not suitable for further clinical development. In addition grade \geq 3 delayed-onset toxicity in this study would imply that the combination of FSRT and TPI 287 is excessively toxic and not suitable for further clinical development. In addition, the results will be discussed with Cortice Bioscience, Protocol Monitoring Committee and IRB and study will be closed. In addition, occurrence of other delayed-onset treatment related grade 3 or higher CNS- toxicity will be monitored closely and reviewed with Protocol Monitoring Committee and IRB to determine whether discontinuation of trial is subsequently warranted.

6. DOSING DELAYS/DOSE MODIFICATIONS/TREATMENT DISCONTINUATION

Dose Level	TPI 287 Dose
-2	$5 \text{ mg/m}^2/\text{dose}$
-1	$7 \text{ mg/m}^2/\text{dose}$
1	14 mg/m ² /dose
2	28 mg/m ² /dose
3	56 mg/m ² /dose
4	85 mg/m ² /dose
5	113 mg/m ² /dose
6	$127.5 \text{ mg/m}^2/\text{dose}$

Table 3. Dose Levels for Dose Modification of TPI 287

Below are dose modification tables for the following adverse events: nausea, vomiting, diarrhea, neutropenia, and thrombocytopenia:

Table 4. Management of Nausea

Nausea	Management/Next Dose for TPI 287
\leq Grade 1	No change in dose
Grade 2	Hold until \leq Grade 1. Resume at same dose level.
Grade 3	Hold [*] until < Grade 2. Resume at one dose level lower, if indicated. [*]
Grade 4	Off protocol therapy
*Patients requiring a delay of ≥ 2 weeks should go off protocol therapy.	
Recommended management: antiemetics.	

Vomiting	Management/Next Dose for TPI 287	
\leq Grade 1	No change in dose	
Grade 2	Hold until \leq Grade 1. Resume at same dose level.	
Grade 3	Hold [*] until < Grade 2. Resume at one dose level lower, if indicated.	
Grade 4	Off protocol therapy	
*Patients requiring a delay of >2 weeks should go off protocol therapy.		
Recommended management: antiemetics.		

Table 5. Management of Vomiting

Table 6. Management of Diarrhea

Diarrhea	Management/Next Dose for TPI 287	
\leq Grade 1	No change in dose	
Grade 2	Hold until \leq Grade 1. Resume at same dose level.	
Grade 3	Hold [*] until < Grade 2. Resume at one dose level lower, if indicated. [*]	
Grade 4	Off protocol therapy	
*Patients requiring a delay of >2 weeks should go off protocol therapy.		
Recommended management: Loperamide antidiarrheal therapy		
Dosage schedule: 4 mg at first onset, followed by 2 mg with each loose motion until diarrhea-		
free for 12 hours (maximum dosage: 16 mg/24 hours)		
Adjunct anti-diarrheal therapy is permitted and should be recorded when used.		

Table 7. Management of Neutropenia

Neutropenia	Management/Next Dose for TPI 287			
≤ Grade 1	No change in dose			
Grade 2	Hold until \leq Grade 1. Resume at same dose level.			
Grade 3	Hold [*] until < Grade 2. Resume at one dose level lower, if indicated.			
Grade 4	Off protocol therapy			
*Patients requiring a delay of >2 weeks should go off protocol therapy.				
Table 8. Management of Thrombocytopenia				
Thrombocytopenia	nia Management/Next Dose for TPI 287			
\leq Grade 1	No change in dose			
Grade 2	Hold until \leq Grade 1. Resume at same dose level.			
Grade 3	Hold [*] until < Grade 2. Resume at one dose level lower, if indicated. [*]			
Grade 4	Off protocol therapy			
*Patients requiring a delay of >2 weeks should go off protocol therapy.				

Infusion interruption is required if a subject experiences a hypersensitivity reaction. A \geq Grade 3 hypersensitivity reaction requires discontinuation. A mild-to-moderate hypersensitivity reaction requires that the infusion rate be slowed (half that of the initial attempt) for the remainder of the trial. The infusion is restarted within 1 hour if the mild-to-moderate signs and symptoms resolve or, if the symptoms take longer to resolve, the infusion is not restarted and the next dose is 1 week at the slower rate.

For each patient, a maximum of one (1) dose reduction of TPI 287 will be allowed after which the patient will be discontinued from the study treatment. If, after interruption of treatment and resolution, treatment is resumed at the same dose and the same toxicity reoccurs with the same severity, next treatment re-initiation must resume at the next dose level irrespective of duration.

7. ADVERSE EVENTS: LIST AND REPORTING REQUIREMENTS

An adverse event (AE) is any unfavorable and unintended sign, symptom, or disease experienced by a study participant while in a clinical study, whether or not considered related to the investigational product. Examples include: reactions or side effects, a pre-existing condition that worsens in severity or frequency, a concurrent illness, an injury, or a clinically significant laboratory abnormality.

7.1 Potential Adverse Events

7.1.1 Radiation

- Early (≤ 30 days from treatment): Expected adverse events include fatigue, headache, neck pain, nausea and vomiting, and lethargy.
- Late (> 30 days from treatment): Possible adverse events include focal neurologic deficits, memory difficulties, dementia, radiation necrosis, and radiation induced neoplasms.

7.1.2 TPI 287

Adverse events (AEs) listed as possibly, probably, or definitely related to TPI 287 for the **single agent** trials **irrespective of dose level and schedule** are summarized below by system organ class:

- Blood and Lymphatic System Disorders: anaemia, leukopenia, lymphopenia, neutropenia, thrombocytopenia
- Cardiac Disorders: tachycardia
- Gastrointestinal Disorders: abdominal pain, abdominal pain lower, abdominal pain upper, ascites, constipation, diarrhoea, dyspepsia, dysphagia, flatulence, gastroenteritis, gastrointestinal bleed, mucositis, nausea, oral pain, stomach discomfort, stomatitis, vomiting
- General Disorders and Administration Site Conditions: asthenia, chest discomfort, chest pain, chills, clinical progression, difficulty in walking, disease progression with higher than expected speed of progression, face edema, fatigue, gait disturbance, mucosal inflammation, edema peripheral, pain, pyrexia

- Hepatobiliary Disorders: hepatic pain, hyperbilirubinaemia
- Immune System Disorders: anaphylactic reaction, hypersensitivity
- Infections and Infestations: bacterial sepsis, Candidiasis, enterococcal infection, eye infection, Herpes zoster, infection
- Injury, Poisoning and Procedural Complications: Head injury
- **Investigations:** ALT increased, AST increased, blood ALP increased, blood bilirubin increased, gamma-glutamyltransferase increased, granulocyte count decreased, haemoglobin decreased, neutrophil count decreased, protein urine, protein urine present, white blood cell count decreased
- Metabolism and Nutrition Disorders: anorexia, decreased appetite, dehydration, failure to thrive, hypokalaemia, hyponatraemia
- Musculoskeletal and Connective Tissue Disorders: arthralgia, back pain, bone pain, facial muscle weakness, muscle spasms, muscular weakness, musculoskeletal pain, myalgia, pain in extremity
- Nervous System Disorders: amnesia, balance disorder, disturbance in attention, dizziness, dysarthria, headache, hypoaesthesia, motor neuropathy, neuropathic pain, neuropathy, neuropathy peripheral, paraesthesia, peripheral sensory neuropathy, peroneal nerve palsy
- Psychiatric Disorders: anxiety, confusion, insomnia, sleep disorder
- Renal and Urinary Disorders: dysuria, haematuria, nephrolithiasis, renal failure, urinary incontinence
- Reproductive System and Breast Disorders: vaginal haemorrhage
- **Respiratory, Thoracic and Mediastinal Disorders:** cough, dysphonia, dyspnoea, pharyngolaryngeal pain, pneumonia, pulmonary embolism, rhinorrhoea
- Skin and Subcutaneous Tissue Disorders: acne, alopecia, dry skin, hyperhidrosis, hypotrichosis, night sweats, pigmentation disorder, rash, skin chapped, skin exfoliation
- Vascular Disorders: deep vein thrombosis, flushing, hypotension, orthostatic hypotension

In a phase I trial of TPI 287 administered weekly for 3 weeks, the most frequent AEs ($\geq 10\%$) considered possibly, probably, or definitely related to TPI 287 were fatigue (40%), nausea

(29%), diarrhoea (21%), anaemia and neuropathy (19%), neuropathy peripheral (17%), vomiting and anorexia (15%), dyspnoea (13%), and dehydration, myalgia, and constipation (10%).

7.2 Adverse Event Characteristics

- CTCAE term (AE description) and grade: The descriptions and grading scales found in the revised NCI Common Terminology Criteria for Adverse Events (CTCAE) version 4.0 will be utilized for AE reporting. http://ctep.cancer.gov/protocolDevelopment/electronic_applications/ctc.htm.
- **Attribution** of the AE:
 - Definite The AE *is clearly related* to the study treatment.
 - Probable The AE is likely related to the study treatment.
 - Possible The AE may be related to the study treatment.
 - Unlikely The AE *is doubtfully related* to the study treatment.
 - Unrelated The AE is clearly NOT related to the study treatment.

For this study, adverse events that are considered by the Investigator to have a Possible, Probable, or Definite relationship to the investigational product are considered to be related to the investigational product.

7.3 Recording & Reporting Adverse Events

AEs will be listed by patient ID number. Deaths and other SAEs will be listed and summarized by patient ID number and treatment duration. Additionally, AEs leading to discontinuations will be listed separately. Incidence of AEs will be summarized by preferred term, maximum grade reported, and relationship to study treatment.

Adverse events should only be recorded by an investigator or by a health-care provider qualified by training and experience. Patients should be asked in an open-ended manner about the occurrence of AEs.

Adverse events will be captured starting from day 1 of receiving TPI 287.

Grade 1 and 2 toxicities unrelated to study treatment will not be captured.

7.4 Adverse Event Reporting Period

Adverse events reporting period will start from day 1 of receiving TPI 287 until the last day of patient's participation in study.

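### After removal from study, new late CNS toxicity, symptomatic necrosis and cause of death are not clearly collected, although the holding and stopping rules depend on them

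*Combined protocol and SAP*

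**What the plan says.** **When collection ends.** Under section 7.4, adverse-event reporting "will start from day 1 of receiving TPI 287 until the last day of" the patient's participation, a term the protocol does not define. Under section 5.7, repeated in footnote d of the section 10 calendar, brain MRI is done "every three months following the end of treatment until the patient is off-study or reaches the 18 month study completion date".

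**Who leaves, and what follows.** The removal criteria in section 5.8 include "Disease progression requiring therapy not allowed in the protocol, including whole brain radiation" and, separately, unacceptable adverse events. For patients who leave, 5.8 gives two provisions: "All trial treatment-related toxicities and SAEs at the time of discontinuation/withdrawal should be followed until resolution or stabilization", and "Patients who are discontinued from the study will still be followed for disease progression". It sets no visit, method or schedule for either.

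**Rules that use late events.** Under section 5.4, a delayed-onset, treatment-related CNS toxicity of grade 3 or higher, at any time during or after the 8-week DLT period, holds escalation and adds three patients at that dose level. Section 5.9 reads "A higher rate of neurologic death (> 14%) or symptomatic brain necrosis (> 10%) in this study" as showing that the combination is too toxic. It states no time window and no denominator.

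**Text pointing the other way.** Section 5.4 says that in-field CNS toxicity seen after 8 weeks will be recorded. Section 5.7 follows patients for 18 months or until death. Footnote g collects survival, disease status and adverse events about every 12 weeks for up to 18 months. Section 7.5 keeps related serious adverse events reportable without a time limit.

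**The concern.** Off treatment and off study are different states, and section 5.8 merges them. All drug and radiation is planned within the first 15 days, while the toxicity of most interest for this combination comes later: section 7.1.1 lists radiation necrosis as a late effect, more than 30 days after treatment. Most of the safety information therefore comes from follow-up, and removal from study is where follow-up becomes uncertain.

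At stake is whether the two late-toxicity rules can work as intended. If new late events in removed patients reach the database only by chance, the holding rule may not fire when it should, and the necrosis and neurologic-death rates may be under-counted. Long-term adverse effects, a secondary endpoint in section 14.1, depend on the same data.

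**Working it through.** The plan states no figure that could be reproduced here, so the check sets what each rule needs against what is provided once a patient has been removed.

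| Event a rule needs | Provided after removal | Left open |
|---|---|---|
| New related delayed CNS toxicity, grade 3+ (5.4) | 5.4: late in-field events will be recorded. 7.5: related serious events are reportable | No visit is clearly scheduled to find them. The open-ended clause in 7.5 depends on the event reaching the investigator. A grade 3 event is not automatically serious |
| Symptomatic necrosis (5.9) | The same two channels. 5.8: followed for progression | The 5.9 rule has no grade or seriousness floor, whereas the late expedited reports in 7.5 are for grade 3 to 5, or grade 2 with hospitalization. Scheduled MRI has ended |
| Neurologic death (5.9) | 5.8: deaths in the trial period or within 30 days of the last dose. 7.5: deaths on study or within 30 days of stopping treatment. Footnote g: survival | A cause for deaths after that time is not expressly required. 5.8 also says that deaths from progression are not serious adverse events |

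**Do section 5.7 and footnote g close the gap?** Two readings are possible.

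1. Participation includes the full 18 months, even for removed patients. Section 7.4 then agrees with footnote g, but the separate and narrower provision in 5.8 becomes hard to explain, and MRI still ends at off-study.
2. Removal ends participation. Section 7.4 then closes adverse-event reporting, 5.8 governs, and footnote g applies only to patients still on study.

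The text does not choose between them.

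**Is the gap open while the rules are in force?** Section 5.4 delays the next level for 8 weeks after the last patient at the current level completes FSRT. If all six levels from level 1 upward are used, there are five waits: 5 × 8 = 40 weeks, before any accrual or treatment time. A patient removed early at level 1 could have a late event well within that time, when it would still bear on escalation.

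**Direction.** The holding rule is triggered by a single event, so an uncollected event can only remove a trigger. For the stopping rule, let p be the true rate and f the share of events not collected. With all treated patients in the denominator, recorded rate = p × (1 − f), which is at most p. The recorded necrosis rate exceeds 10% only if p > 10% / (1 − f), and recorded neurologic death exceeds 14% only if p > 14% / (1 − f). Any f above zero raises the true rate needed to stop.

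**Size.** The documents give neither p nor f for this combination. Section 5.9 gives reference rates for FSRT (13–14% neurologic death, 7.7% symptomatic necrosis). It does not say whether its rates refer to the escalation patients (up to 36), the expansion group (10, including patients treated at the MTD) or everyone. No magnitude follows.

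**The case against.** The best reply is that the protocol, read as a whole, does follow these patients. Section 5.7 promises 18 months of follow-up with toxicity evaluation at each visit and makes no exception for removed patients. Footnote g has no off-study cut-off, although footnote d does. Section 5.4 records late in-field CNS toxicity without an end date. Section 7.5 requires expedited reports of related grade 3 to 5 serious events beyond 30 days, and the holding rule itself counts only related grade 3 or higher events. Removal for progression is also limited to progression that needs therapy outside the protocol.

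Much of this stands. It would be wrong to say that late events in removed patients are lost: serious related events remain reportable, and toxicities present at removal are followed. What remains is that no passage says a removed patient stays in active late-toxicity follow-up, and 5.8 and 7.4 can be read to say the opposite.

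A reader might infer three stronger claims that the documents do not support:

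- That both rules count events at any time. Only the holding rule says so; 5.9 gives no window.
- That PFS and local control are biased favourably. A patient removed for progression has already had the PFS event, and other removed patients are still to be followed for progression. Such a bias is not shown.
- That a figure can be put on the under-count. It would need assumed removal times, onset times and true rates, and it would have to treat capture after removal as zero, contrary to 5.4, 5.8 and 7.5.

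**Conclusion.** The point holds as an inconsistency with a known direction and an unknown size. Scheduled MRI ends at off-study, routine adverse-event reporting ends with participation, and the provisions for removed patients do not clearly include new late CNS toxicity, symptomatic necrosis or cause of death. Under-collection would favour continuing under both rules.

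For the stopping rule, that direction assumes that all treated patients form the denominator. If only patients still under follow-up were counted, the direction would depend on whether removed patients carry higher risk. That is plausible for those removed for brain progression or toxicity, but the documents do not establish it. The protocol should be corrected because the rules concern safety and the remedy is small.

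**What to change.** - In section 5.8, separate off treatment from off study, and define participation in section 7.4 to match.
- State that every treated patient who has not withdrawn consent stays in the footnote g follow-up, about every 12 weeks to month 18 or death, whatever the reason for removal.
- At each contact, collect grade 3 or higher CNS events, symptomatic necrosis, and death with its cause. Record the results of any brain imaging done in routine care. Additional protocol MRI after removal is not needed for this change.
- Reconcile sections 5.4, 5.7, 5.8, 5.9, 7.4 and 7.5 with calendar footnotes d and g, including the statements on which deaths are reported. State the time window and denominator to which the 5.9 rates refer.

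The cost is a wording amendment plus some extra contacts and records in removed patients, on an interval the calendar already uses.

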7.5 Immediate Reporting of Serious Adverse Event

Any serious adverse event including, death due to any cause, pregnancy, which occurs to any patient treated on study or within 30 days following cessation of treatment, whether or not related to the investigational product, must be reported to Cortice Biosciences within 24 hours.

It is the Investigator's responsibility to report serious adverse events to the regulatory agencies and Institutional Review Board (IRB) according to the requirements of the IRB/IEC.

Additionally, any serious adverse event considered by an investigator to be possibly, probably, or definitely related to the study treatment that is brought up to the attention of the investigator at any time outside of the time period specified in Table.9 must be reported immediately to Cortice Biosciences.

All patients with serious adverse events must be followed up for outcome.

Serious Adverse Events (SAE) are:

Any untoward medical occurrences that at any dose:

- Results in death
- Is life threatening
- Requires inpatient hospitalization or prolongation of existing hospitalization
- Results in persistent or significant disability/incapacity, or,
- Is a congenital anomaly/birth defect

The onset date of an SAE is defined as the date on which it met the criteria for an SAE; e.g., the date of admission to a hospital. The end date is the date on which it no longer met the criteria for an SAE, e.g., the date that the patient was discharged from a hospital.

Expedited Reporting Guidelines

Note: A death on study requires both routine and expedited reporting regardless of causality, unless as noted below. Attribution to treatment or other cause must be provided.

 Table 9. Expedited Reporting Requirements for Adverse Events that Occur within 30

Days of the Last Administration of TPI 287

FDA REPORTING REQUIREMENTS FOR SERIOUS ADVERSE EVENTS (21 CFR Part 312)

NOTE: Investigators **MUST** immediately report to the sponsor **ANY** Serious Adverse Events, whether or not they are considered related to the investigational agent(s)/intervention (21 CFR 312.64)

An adverse event is considered serious if it results in ANY of the following outcomes:

- 1) Death
- 2) A life-threatening adverse event
- 3) An adverse event that results in inpatient hospitalization or prolongation of existing hospitalization for ≥ 24 hours
- 4) A persistent or significant incapacity or substantial disruption of the ability to conduct normal life functions
- 5) A congenital anomaly/birth defect.
- 6) Important Medical Events (IME) that may not result in death, be life threatening, or require hospitalization may be considered serious when, based upon medical judgment, they may jeopardize the patient or subject and may require medical or surgical intervention to prevent one of the outcomes listed in this definition. (FDA, 21 CFR 312.32; ICH E2A and ICH E6).

ALL SERIOUS adverse events that meet the above criteria MUST be immediately reported to the Cortice bioscience within the timeframes detailed in the table below.

Hospitalization	Grade 1 and Grade 2 Timeframes	Grade 3-5 Timeframes		
Resulting in Hospitalization ≥ 24 hrs	10 Calendar Days	24-Hour 5 Calendar		
Not resulting in Hospitalization ≥ 24 hrs	Not required	Days		

Expedited AE reporting timelines are defined as:

- "24-Hour; 5 Calendar Days" The AE must initially be reported within 24 hours of learning of the AE, followed by a complete expedited report within 5 calendar days of the initial 24-hour report.
- "10 Calendar Days" A complete expedited report on the AE must be submitted within 10 calendar days of learning of the AE.

Serious adverse events that occur more than 30 days after the last administration of investigational agent/intervention and have an attribution of possible, probable, or definite require reporting as follows:

Expedited 24-hour notification followed by complete report within 5 calendar days for:

• All Grade 3, 4, and Grade 5 AEs

Expedited 10 calendar day reports for:

• Grade 2 AEs resulting in hospitalization or prolongation of hospitalization

